9.4. Pharmacodynamic Analysis

The pharmacodynamic (PD) analysis population is defined as all randomized subjects treated who have at least one PD assessment in at least one cohort. PD assessments will include, but not limited to, CCI soluble protein analytes, whole-blood RNA (inflammation and disease-related) and responses to vaccines. The data will be summarized and plotted by treatment group and sampling time. Further details will be documented in the SAP.

CCI

CCI

9.6. Safety Analysis

Adverse events, ECGs, blood pressure, pulse rate, oral temperature, continuous cardiac monitoring, and safety laboratory data will be reviewed and summarized on an ongoing basis during the study to evaluate the safety of subjects. Any clinical laboratory, ECG, vital sign abnormalities of potential clinical concern will be described. Safety data will be presented in tabular and/or graphical format and summarized descriptively, where appropriate.

Immunogenicity (ADA, NAb) results will be listed and summarized by cohorts and time points. Subject level immune response will also be summarized by cohorts. Effect of positive ADA and neutralizing immune response on safety, PD and PK may be assessed, if appropriate.

Incidence of viral infections or change in baseline of viral loads (CMV, VZV, EBV, and HSV-1/2) if they occur, will be summarized by treatment group.

Medical history and physical examination and neurologic examination information, as applicable, collected during the course of the study will be considered source data and will not be required to be reported, unless otherwise noted. However, any untoward findings identified on physical and/or neurologic examinations conducted during the active collection period will be captured as an adverse event, if those findings meet the definition of an adverse event. Data collected at Screening that are used for inclusion/exclusion criteria, such as laboratory data, ECGs and vital signs will be considered source data, and will not be required to be reported, unless otherwise noted. Demographic data collected at Screening will be reported.

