2. STUDY OBJECTIVES AND ENDPOINTS

Primary Objective:	Primary Endpoints:

 To evaluate the safety and tolerability of single and multiple ascending intravenous (IV) and subcutaneous (SC) doses of PF-06835375 in subjects with SLE and RA. 	
 Incidence of dose limiting or treatment related adverse events (AEs). Incidence, severity and causal relationship of treatment emergent AEs (TEAEs) and withdrawals due to treatment emergent adverse events. Incidence of abnormal chemistry, hematology, and urinalysis laboratory findings through the end of study. Abnormal and clinically relevant changes in vital signs and electrocardiogram (ECG) parameters. Incidence of infections.
Secondary Objectives:	Secondary Endpoints:

 To evaluate the effect of PF-06835375 on depletion of circulating CXCR5 positive B cells and cTfh cells in subjects with SLE and RA. To characterize pharmacokinetics (PK) profile of PF-06835375 in subjects with SLE and RA. 	
 Change from baseline in the number of circulating CXCR5 positive B cells and cTfh cells on Day 29 single dose of PF-06835375 and at Week 8 following multiple doses of PF-06835375. Serum PF-06835375 PK parameters after single and multiple doses: 
 Single Ascending Dose Phase: C_{max}, T_{max}, AUC_{inf}, AUC_{last}. Multiple Ascending Dose Phase: 
 First Dose: C_{max}, T_{max}, AUC_{tau}. Multiple Dose: C_{max}, T_{max}, AUC_{last}, AUC_{tau}, C_{min} and observed accumulation ratio (R_{ac}), peak-to-trough ratio (PTR).

 To evaluate immunogenicity of PF-06835375 in subjects with SLE and RA. 	
 Incidence of development of anti-drug antibodies (ADAs)/neutralizing antibodies (Nabs).
CCI	

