7.1.11. Monitoring for Infections

Subjects will be monitored for development of any infection (viral, bacterial, and fungal) at each visit. Infections will be classified as either treated or non-treated infections. All treated infections occurring during the study require identification of the causative organism, if feasible, whether by culture, antigen assay, serology, etc. (as appropriate) and the results (eg, any identified organisms or absence of growth) recorded in the CRF.

Treated infections are infections that:

- Require antimicrobial therapy by any route of administration or;
- Require any surgical intervention (eg, incision and drainage).

A subject, who experiences an infection associated with SAE should not receive further dose(s) of investigational product. Furthermore, a subject, who requires oral or parenteral antimicrobial therapy (with the exception of mild vulvovaginal/urogenital infections), should only be administered further dose(s) of investigational product after consultation with sponsor clinician or medical monitor.

A serious infection should be reported as a SAE and should be listed as the reason for discontinuation in the CRF. All serious infections occurring during the study should undergo appropriate laboratory investigations, including culture, and the results (eg, any identified organisms or absence of growth) should be recorded in the CRF.

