7.1.15. Viral Surveillance

Blood samples for possible analysis of cytomegalovirus (CMV), Epstein-Barr virus (EBV), herpes simplex virus type 1 & 2 (HSV-1, HSV-2) and varicella-zoster virus (VZV) will be collected according to the times outlined in the [Schedule of Activities](#). Details regarding the collection, processing, storage and shipping of the blood samples will be provided in the lab manual.

Note: Due to delayed reporting times for these assays, the results might not be available along with the other study tests.

In addition to time points specified, a blood sample for viral surveillance sample may also be taken at the time of an AE, as clinically appropriate.

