6.2. Safety Endpoints

In this section, the safety endpoints that will be measured during the study are detailed. Where applicable, details of the endpoints to be derived and definition of baseline are also provided.

The following data are considered in standard safety summaries (see protocol for collection days and list of parameters):

- *adverse events*,
- *laboratory data*,
- *vital signs data*,
- *ECG results*.

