8.3.8. Other Safety Data

None.

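### Infection incidence is a primary endpoint, but the SAP leaves it to standard adverse event tables, where crude proportions are biased against the drug because follow-up depends on B-cell recovery

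*Protocol*

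**What the plan says.** Protocol Section 2 gives "Incidence of infections" as a separate primary endpoint, next to the bullets on treatment-emergent adverse events, laboratory findings, vital signs and ECG. Protocol 9.6 adds that "Incidence of viral infections or change in baseline of viral loads" (for CMV, VZV, EBV and HSV-1/2), where they occur, are to be summarised by treatment group. Protocol 7.1.15 is more cautious about the samples behind this, which it describes as "Blood samples for possible analysis of cytomegalovirus (CMV), Epstein-Barr virus (EBV" and the other listed viruses).

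SAP 6.2 introduces its safety endpoints with "The following data are considered in standard safety summaries" and names four: adverse events, laboratory data, vital signs and ECG. SAP 6.2.5 says that further safety data will be listed where needed. SAP 8.3.4 sends adverse events to the sponsor's reporting standards and adds specific outputs for infusion reactions, injection site reactions and possible cytokine release. It adds none for infections. Under "8.3.8. Other Safety Data" the entry is the single word None.

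Three further rules decide what an adverse event table would count:

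- SAP 6.2.1 treats any event after the start of treatment as treatment emergent, including events in follow-up, and sets no cut-off.
- Protocol 8.1.4 collects events for at least 90 days after the last dose, and to the end-of-study visit for subjects who remain longer.
- Protocol 3.5 ties the end-of-study visit to B-cell counts.

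**The concern.** There are two problems, and the second carries more weight.

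The first is traceability. A named primary endpoint and a by-treatment summary stated in the protocol have no counterpart in the SAP sections where they belong. Protocol Section 9 lets the SAP modify the protocol's analyses, but major changes to primary endpoint analyses must also be reflected in an amendment. If the silence is deliberate, the documents need reconciling.

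The second is bias. If infections are read only from a standard table of n (%), the groups are compared over different lengths of time, and the length depends on the drug's own pharmacodynamic effect. Subjects with longer depletion are watched for longer and collect more infections even if the drug does nothing to infection risk. The table could then show an excess on active treatment, or an apparent dose trend, produced by follow-up alone. Protocol 1.6 discusses infections, including fatal ones, as a known risk of B-cell depleting agents, so readers will look at this comparison closely.

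**Working it through.** **Step 1: protocol against SAP.**

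| Protocol commitment | Matching SAP text |
|---|---|
| Infection incidence as a primary endpoint (Section 2) | None by name in 6.2 or 8.3; covered only within general adverse event reporting (8.3.4) |
| Viral infections or viral-load change by treatment group, if they occur (9.6) | None by name; 6.2.5 offers listings, 8.3.8 says None |

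The visible SAP text does not mention infection, viral surveillance or viral load. Parts of SAP 6.1, 6.4 to 6.6 and 8.2.3 are redacted, and SAP Section 1 refers to a separate bSAP. SAP 6.2 and 8.3 show no redaction, and Section 1 connects the bSAP with exploratory objectives and the endpoint mapping in 6.4 and 6.5, not with safety.

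**Step 2: who is followed for how long.**

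- Entry requires a B-cell count of at least 80 cells/µL (Protocol 4.2, criterion 22).
- Discharge at Week 16 requires either at least 80 cells/µL, or at least 50% of baseline and stable or increasing since Week 12 (Protocol 3.5). A placebo subject who keeps the entry level therefore qualifies.
- The end-of-study phone visit follows about 1 to 2 weeks later, so early leavers have roughly 17 weeks of collection.
- Others continue every 4 weeks to Week 52, then every 12 weeks (Protocol 3.1). A subject discharged on a new stable but lower level cannot leave before the Week 24 result is available (Protocol 3.5).
- The expected stay is about 6 to 12 months including screening (Protocol 3.1).

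**Step 3: size of the artefact under no drug effect.** The documents give no infection rate, so the rates r are assumed. The 40 weeks is also assumed, as a value within the expected stay. With a constant rate r per year and follow-up of t weeks, the probability of at least one infection is

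risk = 1 − exp(−r × t/52).

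Worked case, r = 0.8: at 17 weeks, 1 − exp(−0.8 × 17/52) = 1 − exp(−0.2615) = 0.230. At 40 weeks, 1 − exp(−0.8 × 40/52) = 1 − exp(−0.6154) = 0.460.

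The same formula with 24 and 52 weeks shows how far the result depends on the assumed duration:

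| Rate per year (equal in both groups) | 17 weeks | 24 weeks | 40 weeks | 52 weeks |
|---|---|---|---|---|
| 0.4 | 12% | 17% | 26% | 33% |
| 0.8 | 23% | 31% | 46% | 55% |
| 1.2 | 32% | 43% | 60% | 70% |

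**Step 4: what a common window does.** Over 16 weeks for everyone, r = 0.8 gives 1 − exp(−0.8 × 16/52) = 1 − exp(−0.2462) = 0.218 in both groups, so the difference disappears. A rate per person-year also returns 0.8 in both groups, whatever the follow-up.

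**The case against.** The strongest reply is that the endpoint is analysed. It is stated as incidence, with no window, rate or subclass. Infections are recorded as adverse events, and SAP 8.3 summarises safety data by treatment, so a standard table would show an infections class. That stands. A reader might infer from the None in SAP 8.3.8 that the primary endpoint has no analysis at all, and the documents do not support that.

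The viral commitment is also narrower than it may look. Protocol 9.6 says infections or loads, conditional on occurrence, and Protocol 7.1.15 speaks of possible analysis. A reader might infer an unconditional promise of both summaries, but the text does not make one. Protocol Table 3 places viral surveillance among the laboratory tests, and SAP 8.3.5 summarises laboratory data by treatment, so coverage there is arguable. Against this, SAP 6.2.2 describes only haematology, clinical chemistry and urinalysis.

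Protocol 7.1.11 states "Infections will be classified as either treated or non-treated infections", and it is tempting to call the missing split an omission. No section promises a summary by that class. Nor does Protocol 1.6 rank infection above the other risks it describes.

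On bias, the rates and the 40 weeks are assumptions, and active subjects at low doses may recover by Week 16, so the contrast is between recovered and depleted subjects rather than strictly placebo and active. The study is descriptive, and one event among 3 active subjects is already 33%. All this limits how precisely the artefact can be stated. It leaves the mechanism and its direction intact.

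**Conclusion.** The point holds in limited form. SAP 6.2 and 8.3 specify no analysis for infections beyond general adverse event reporting and do not carry forward the conditional viral summary of Protocol 9.6. The proportion that would be reported is biased against the drug at any positive infection rate, provided depleted subjects are followed for longer than recovered ones, as Protocol 3.5 arranges.

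Under equal rates of 0.4 to 1.2 per year and 17 versus 40 weeks, the crude risk is roughly doubled: 12% vs 26% at the low end and 32% vs 60% at the high end. This is an illustration resting on a constant rate and assumed durations, not an estimate for this trial. A reader might infer that the plan could hide an infection signal. The direction is the opposite: unequal follow-up overstates infection on active treatment. The harm is a misleading comparison and possibly a spurious dose trend.

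**What to change.** In SAP 8.3.4 or 8.3.8, define which events count as infections and add:

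1. Infections, all and serious, as n (%) by treatment group through the common Week 16 window.
2. The infection rate per person-year by treatment group over all follow-up, stating whether first or all events are counted and showing person-time.
3. Where viral assays are run, the by-treatment summary of viral infections or viral-load change set out in Protocol 9.6.

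Align SAP 6.2.5 and 8.3.8 with these additions so that one section does not offer listings while the other says None. A treated/non-treated split is optional. No hypothesis test is needed.

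The cost is two or three descriptive tables from data already collected. With 3 to 6 active subjects planned per cohort, cohort-level figures will be imprecise and should be presented as such.

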9.6.1. Electrocardiogram (ECG) Analysis

Changes from baseline for the ECG parameters QT interval, heart rate, QTc interval, PR interval and QRS interval will be summarized by treatment and time.

The number (%) of subjects with maximum post dose QTc values and maximum increases from baseline in the following categories will be tabulated by treatment:

Table 7. Safety QTc

	Borderline (msec)	Prolonged (msec)
Absolute Value	$\geq 450 - < 480$	≥ 480
Absolute Change	30- < 60	≥ 60

In addition, the number of subjects with corrected and uncorrected QT values ≥ 500 msec will be summarized.

If more than one ECG is collected at a nominal time after dose administration (for example, triplicate ECGs), the mean of the replicate measurements will be used to represent a single observation at that time point. If any of the three individual ECG tracings has a QTc value ≥ 500 msec, but the mean of the triplicates is not ≥ 500 msec, the data from the subject's individual tracing will be described in a safety section of the CSR in order to place the ≥ 500 msec value in appropriate clinical context. However, values from individual tracings within triplicate measurements that are ≥ 500 msec will not be included in the categorical analysis unless the average from the triplicate measurements is also ≥ 500 msec. Changes from baseline will be defined as the change between postdose QTc value and the average of the pre-dose triplicate values on Day 1. The average of the pre-dose triplicate QTc values on Day 1 will serve as each subject's baseline QTc value. Standard algorithms and reporting formats will be applied.

In addition, an attempt may be made to explore and characterize the relationship between serum concentration and appropriately corrected QT interval length. The results from this analysis will be reported separately from CSR.

9.7. Interim Analysis

No formal interim analysis will be conducted for this study. However, as this is a sponsor-open study, the sponsor may conduct unblinded reviews of the data during the course of the study for the purpose of safety assessment, facilitating dose-escalation decisions, facilitating PK/PD modeling, and/or to support clinical development.

9.8. Data Monitoring Committee

This study will not use a data monitoring committee. Ongoing safety reviews in support of dose escalation and during the study will be conducted by blinded and unblinded personnel as described in [Section 3.4](#).

10. QUALITY CONTROL AND QUALITY ASSURANCE

Pfizer or its agent will conduct periodic monitoring visits during study conduct to ensure that the protocol and Good Clinical Practices (GCPs) are being followed. The monitors may review source documents to confirm that the data recorded on CRFs are accurate. The investigator and institution will allow Pfizer monitors/auditors or its agents and appropriate

regulatory authorities direct access to source documents to perform this verification. This verification may also occur after study completion.

During study conduct and/or after study completion, the investigator site may be subject to review by the IRB/EC, and/or to quality assurance audits performed by Pfizer, or companies working with or on behalf of Pfizer, and/or to inspection by appropriate regulatory authorities.

The investigator(s) will notify Pfizer or its agents immediately of any regulatory inspection notification in relation to the study. Furthermore, the investigator will cooperate with Pfizer or its agents to prepare the investigator site for the inspection and will allow Pfizer or its agent, whenever feasible, to be present during the inspection. The investigator site and investigator will promptly resolve any discrepancies that are identified between the study data and the subject's medical records. The investigator will promptly provide copies of the inspection findings to Pfizer or its agent. Before response submission to the regulatory authorities, the investigator will provide Pfizer or its agents with an opportunity to review and comment on responses to any such findings.

It is important that the investigator(s) and their relevant personnel are available during the monitoring visits and possible audits or inspections and that sufficient time is devoted to the process.

11. DATA HANDLING AND RECORD KEEPING

11.1. Case Report Forms/Electronic Data Record

As used in this protocol, the term CRF should be understood to refer to either a paper form or an electronic data record or both, depending on the data collection method used in this study.

A CRF is required and should be completed for each included subject. The completed original CRFs are the sole property of Pfizer and should not be made available in any form to third parties, except for authorized representatives of Pfizer or appropriate regulatory authorities, without written permission from Pfizer.

The investigator has ultimate responsibility for the collection and reporting of all clinical, safety, and laboratory data entered on the CRFs and any other data collection forms (source documents) and ensuring that they are accurate, authentic/original, attributable, complete, consistent, legible, timely (contemporaneous), enduring, and available when required. The CRFs must be signed by the investigator or by an authorized staff member to attest that the data contained on the CRFs are true. Any corrections to entries made in the CRFs or source documents must be dated, initialed, and explained (if necessary) and should not obscure the original entry.

In most cases, the source documents are the hospital or the physician subject chart. In these cases, data collected on the CRFs must match the data in those charts.

In some cases, the CRF may also serve as the source document. In these cases, a document should be available at the investigator site and at Pfizer that clearly identifies those data that will be recorded on the CRF, and for which the CRF will stand as the source document.

11.2. Record Retention

To enable evaluations and/or inspections/audits from regulatory authorities or Pfizer, the investigator agrees to keep records, including the identity of all participating subjects (sufficient information to link records, eg, CRFs and hospital records), all original signed informed consent documents, copies of all CRFs, safety reporting forms, source documents, and detailed records of treatment disposition, and adequate documentation of relevant correspondence (eg, letters, meeting minutes, and telephone call reports). The records should be retained by the investigator according to the ICH guidelines, according to local regulations, or as specified in the clinical study agreement (CSA), whichever is longer.

If the investigator becomes unable for any reason to continue to retain study records for the required period (eg, retirement, relocation), Pfizer should be prospectively notified. The study records must be transferred to a designee acceptable to Pfizer, such as another investigator, another institution, or an independent third party arranged by Pfizer.

Investigator records must be kept for a minimum of 15 years after completion or discontinuation of the study or for longer if required by applicable local regulations.

The investigator must obtain Pfizer's written permission before disposing of any records, even if retention requirements have been met.

12. ETHICS

12.1. Institutional Review Board/Ethics Committee

It is the responsibility of the investigator to have prospective approval of the study protocol, protocol amendments, informed consent documents, and other relevant documents, eg, recruitment advertisements, if applicable, from the IRB/EC. All correspondence with the IRB/EC should be retained in the investigator file. Copies of IRB/EC approvals should be forwarded to Pfizer.

The only circumstance in which an amendment may be initiated prior to IRB/EC approval is where the change is necessary to eliminate apparent immediate hazards to the subjects. In that event, the investigator must notify the IRB/EC and Pfizer in writing immediately after the implementation.

12.2. Ethical Conduct of the Study

The study will be conducted in accordance with the protocol, legal and regulatory requirements, and the general principles set forth in the International Ethical Guidelines for Biomedical Research Involving Human Subjects (Council for International Organizations of Medical Sciences 2002), ICH Guideline for Good Clinical Practice, and the Declaration of Helsinki.

12.3. Subject Information and Consent

All parties will ensure protection of subject personal data and will not include subject names or other identifiable data in any reports, publications, or other disclosures, except where required by law.

When study data are compiled for transfer to Pfizer and other authorized parties, subject names, addresses, and other identifiable data will be replaced by numerical codes based on a numbering system provided by Pfizer in order to de-identify study subjects. The investigator site will maintain a confidential list of subjects who participated in the study, linking each subject's numerical code to his or her actual identity. In case of data transfer, Pfizer will maintain high standards of confidentiality and protection of subjects' personal data consistent with applicable privacy laws.

The informed consent documents and any subject recruitment materials must be in compliance with ICH GCP, local regulatory requirements, and legal requirements, including applicable privacy laws.

The informed consent documents used during the informed consent process and any subject recruitment materials must be reviewed and approved by Pfizer, approved by the IRB/EC before use, and available for inspection.

The investigator must ensure that each study subject, is fully informed about the nature and objectives of the study and possible risks associated with participation.

The investigator, or a person designated by the investigator, will obtain written informed consent from each subject before any study-specific activity is performed. The investigator will retain the original of each subject's signed consent document.

12.4. Reporting of Safety Issues and Serious Breaches of the Protocol or ICH GCP

In the event of any prohibition or restriction imposed (ie, clinical hold) by an applicable regulatory authority in any area of the world, or if the investigator is aware of any new information that might influence the evaluation of the benefits and risks of the investigational product, Pfizer should be informed immediately.

In addition, the investigator will inform Pfizer immediately of any urgent safety measures taken by the investigator to protect the study subjects against any immediate hazard, and of any serious breaches of this protocol or of ICH GCP that the investigator becomes aware of.

